1. ABSTRACT

Non-adherence to antiepileptic drugs (AEDs) is a common problem (i.e., 58% of patients have some level of non-adherence) for young children with newly diagnosed epilepsy, with potentially devastating consequences. AED non-adherence is associated with a 3-fold increased risk of seizures, poor quality of life, inaccurate clinical decision-making, and higher health care utilization and costs. One of the primary barriers to adherence is forgetting, which may be particularly amenable to mHealth (mobile technology in healthcare) interventions. Despite the critical need to develop and implement interventions to improve adherence, there are few family-based interventions for young children with epilepsy and their families, with the exception of our work. Although highly promising, this intervention requires six in-person sessions, which can be impossible for families who lack routine access to tertiary specialty care due to time, financial, or transportation constraints. Thus, unmet medical and psychosocial needs of the underserved pediatric epilepsy population are perpetuated and compounded by limited access to this state of the art care. Our overall goal in this multisite study is to test an mHealth adherence intervention that is easily accessible using a stepped up care model based on individual needs. This stepped up care model will conserve patient, family, and provider time, costs and resources. We have completed the first phase of this work and incorporated the feedback we gathered from caregivers during focus groups and usability studies to develop the individualized adherence feedback reports, and all modules of the intervention (e.g., education and problem-solving web-based modules) to improve adherence.

The second phase of this study will consist of a 2-stage, sequential, multiple-assignment, randomized trial (SMART) to evaluate the effectiveness of mHealth intervention strategies for improving AED adherence in parents/legal guardians of young children with epilepsy. We plan to recruit a total of 600 participants across all collaborating study sites, with approximately 150 at each site. Enrolled caregivers will complete study questionnaires and be asked to start using electronic adherence monitors (e.g., pillbox or pill bottle) at the time of data enrollment during the baseline period. Only participants who demonstrate adherence $\leq 95\%$ will be randomized to either the control group or treatment group in Stage 1. At the end of Stage 1, participants who demonstrate adherence $\leq 95\%$ will undergo a second randomization to either stay in their original group or receive the stepped up intervention. The primary outcome is electronically-monitored adherence. Secondary outcomes include seizure severity/frequency, quality of life and healthcare utilization. These data will then be examined, analyzed, and used to evaluate study aims including efficacy, effectiveness, and predictors of treatment responsiveness.

2. PURPOSE OF STUDY

The purpose of this study is to evaluate the efficacy of a mHealth adherence intervention in caregivers of children with newly diagnosed epilepsy, to compare the effectiveness of three different intervention strategies, and to identify predictors of treatment responsiveness.

Specifically, our aims are as follows:

Aim 1: Examine the efficacy of the mHealth adherence intervention in caregivers of children (ages 2-12) with newly diagnosed epilepsy (< 2 years) on electronically monitored adherence.

Aim 2: To compare the effectiveness of the three intervention strategies on adherence, seizure severity/frequency, quality of life, and healthcare utilization at 1-, 6-, and 12-months post-intervention.

Aim 3: To identify individual and family characteristics that predict responsiveness to the three intervention strategies and to derive an optimal, adaptive intervention strategy for tailoring selection of initial and subsequent intervention in the case of nonresponse based on individual characteristics.

3. BACKGROUND

Children with epilepsy represent a high-risk and underserved population. Epilepsy is a common chronic neurological condition that affects 1%² of the US population and disproportionately affects children³ (750,000 youth).^{4,5} Epilepsy is characterized by recurrent unprovoked seizures. Children with epilepsy are 3-6 times more likely to have neurodevelopmental (e.g., autism) disorders,⁶ and/or psychological (e.g., depression) comorbidities than the general population and children with non-neurological conditions.⁷⁻¹⁰ Children with epilepsy are at 4-fold increased risk¹¹ for premature death, with higher risk linked to comorbidities.¹¹⁻¹⁴ Further, 54-59% of youth with epilepsy live in poverty (i.e., household income < \$36,000),¹⁵⁻¹⁷ 53% have public insurance,¹⁶ 32% live in rural locations,¹⁷ and 64% of caregivers have low health literacy.¹⁵ Unfortunately, federal programs/agencies have historically allocated considerably less funding to epilepsy than far less prevalent conditions.¹⁸

Despite the heavy burden of epilepsy⁴, children with epilepsy are an underserved and vulnerable population with many unmet medical and behavioral health needs.^{18,34-39} Only 30% of children with epilepsy receive psychosocial/behavioral health care including adherence interventions, likely due to barriers inherent in the delivery or context of the intervention itself.^{34,35} Furthermore, ~60% of children with newly diagnosed epilepsy and their caregivers demonstrate non-adherence,⁴⁰ a significant risk factor for poor health outcomes. In particular, children with lower socioeconomic,⁴⁰ African American race status,⁴¹ and lower parental health literacy¹⁵ are at increased risk for antiepileptic drug (AED) non-adherence. This may be due to greater concerns about the AEDs, including whether they are more harmful than beneficial.⁴² Similarly, lower socioeconomic status, African American race, and rural residency are associated with increased risk of early death,^{11,17} likely due to lack of resources and access to comprehensive multidisciplinary epilepsy care.^{38,43} Overall, these findings highlight that children with epilepsy are an underserved population, with some subgroups exhibiting multiple risk-factors and vulnerabilities contributing to non-adherence.

Consequences of non-adherence are significant. Non-adherence makes seizure control more difficult,^{44,45} leading to increased healthcare utilization,^{46,47} unnecessary AED changes,⁴⁸ and even death.¹³ Children who demonstrate AED non-adherence in the first six months of treatment are >3 times more likely to have seizures 4-years post-diagnosis compared to children with near-perfect adherence.⁴⁵ Our research also demonstrates that both biology and adherence play critical roles in health outcomes and that variable non-adherence appears to increase the likelihood of having seizures.⁴⁴ Non-adherence has also been shown to impact patient-reported outcomes (e.g., quality of life).⁴⁹ Despite the known impact of non-adherence on health and patient-reported outcomes for children with epilepsy, few adherence interventions have been developed.

Adherence interventions are critically necessary, need to target caregivers, and must be individualized. A 2017 Cochrane review indicated a lack of well-designed randomized controlled clinical trials (RCT) to improve adherence in epilepsy, especially in young children.⁵⁰

Based on this Cochrane review, we are the only researchers to develop and pilot test interventions for young children with epilepsy and their caregivers. In our first pilot study, families receiving an education and problem-solving intervention had a 32% adherence improvement from baseline to post-intervention.⁵¹ In the second pilot study, statistically significant differences between treatment versus controls were noted following the second problem-solving session.⁵² Both interventions focused on education and problem-solving and demonstrated excellent preliminary efficacy and feasibility/acceptability among families. The problem-solving approach targeted family-specific adherence barriers, which varied by family, suggesting the need for individualized treatment. Furthermore, improvement in adherence varied based on the number and types of barriers endorsed. For example, some families who endorsed forgetting chose text reminders and had significantly improved adherence while others required further problem-solving around more difficult barriers, such as behavior problems. This highlights the need for both tailored and stepped up care to match the family's specific barriers and needs. Further, scheduling face-to-face sessions was challenging; thus, a model utilizing mHealth could improve dissemination of adherence interventions. The proposed intervention will translate the education and problem-solving content from our pilot studies to mHealth modules for families. Notably, these modules will be provided in a stepped up care approach, such that non-responders will receive more time and resource-intensive problem-solving sessions followed by therapist-guided telehealth sessions to address family-identified adherence barriers.

Targets for adherence intervention. Previously identified targets for adherence intervention in young children with epilepsy and their caregivers include epilepsy knowledge, adherence barriers (e.g., forgetting to take AEDs), problem-solving, communication, and effective self-management skills.⁵²⁻⁵⁴ These studies highlight that we have identified optimal targets (mechanisms of action) for the proposed intervention.

Knowledge: Caregivers of children with epilepsy reported lacking information about their child's epilepsy.⁵⁵ Only 29% of caregivers of children with epilepsy knew the name or dose of their child's AED,⁵⁶ and some did not believe that AEDs were beneficial.⁵⁷⁻⁵⁹ Increasing adult knowledge of epilepsy and the perceived benefits of AEDs may be associated with adherence gains.⁶⁰⁻⁶³ However, knowledge is necessary but not sufficient to improve and sustain treatment adherence.⁶⁴⁻⁶⁶ Teaching children and families the skills to apply this knowledge (e.g., how to implement an AED titration schedule, when to take AEDs) is critical to improve adherence and will be provided to both control and treatment groups in the current proposal.

Forgetting: Forgetting is a major adherence barrier across many pediatric and adult chronic conditions.^{42,59} mHealth solutions may address this barrier because 92% of adults have cell phones (67% are smartphones), with 97% using text messaging and 89% using it for the internet.⁶⁷ Individuals with lower income or of minority status increasingly depend on smartphones for internet access.⁶⁷ As such, the number of mHealth tools focused on improving adherence via automated digital reminders have increased, with 160 commercial adherence tools currently available.⁶⁸ These reminder systems have high feasibility, satisfaction, cultural acceptability, ease of use, and are low-cost. A recent meta-analysis of text-messaging interventions to improve adherence revealed significant benefits in 18 of 29 studies; however, only three of the 18 studies were pediatric and none were in epilepsy.⁶⁹ Another review of electronic medication packaging and digital reminders found variable improvements in adherence, but studies lacked scientific rigor (e.g., small sample, non-randomization) and were primarily adult-focused.⁷⁰ Notably, both reviews concluded that long-term rigorous RCTs, with objective adherence measures, are still needed to determine the efficacy of mHealth adherence interventions, especially in pediatrics. Further, a 2017 review of all mHealth pediatric interventions found that caregiver involvement was a significant positive moderator of treatment effects, suggesting the need to focus on caregivers of children with chronic diseases.⁷¹

Individualized Adherence Feedback: These meta analyses also found that the best performing interventions tailored content to the specific needs of an individual,⁶⁹ indicating that

individualized adherence feedback is critical to the success of this type of intervention. For example, an HIV adherence intervention study that provided electronically-monitored adherence feedback to non-adherent patients (< 95%) found a 10% improvement (i.e., 86.8% to 96.5%) in the treatment group versus 1% improvement (83.8% to 84.5%) in the control group.⁷² Interventions using individualized feedback in pediatric asthma have also resulted in short-term adherence improvements.^{73,74} Several adult studies have demonstrated significant improvements in adherence relative to control conditions with the provision of individualized adherence feedback,⁷⁵ suggesting this is a beneficial method to improve adherence in caregivers of children with epilepsy.

Problem-solving: Beyond forgetting, caregivers of children with epilepsy identify general barriers, including competing extracurricular activities, difficulty swallowing pills, and poor family communication, as well as epilepsy-specific barriers such as AED side effects and the stigma associated with having epilepsy and taking AEDs.⁵⁹ Tailored problem-solving around these more complex adherence barriers can be provided to children with epilepsy and their caregivers who most need it. For example, if caregivers report oppositional behaviors as a primary barrier, problem-solving would focus on identifying solutions, such as giving rewards for taking AEDs, to reduce oppositional behaviors. Our intervention studies demonstrate that face-to-face problem-solving is efficacious in improving adherence but does not reach many families with children with epilepsy. Thus, one goal of this proposal is to translate problem-solving content into a mHealth module with therapist-guided telehealth sessions. These problem-solving sessions require trained professionals; thus, this component is reserved for participants who are non-responsive to the initial, less time-intensive and costly adherence intervention dose (e.g., automated digital reminders, individualized adherence feedback) and need stepped-up, tailored care. Because clinician time is not required for the initial intervention, our intervention has considerable potential for sustainability and broad dissemination for epilepsy and other chronic conditions.

Overall Impact. If successful, the results of this study would have a large impact on pediatric epilepsy and other chronic pediatric conditions, with the potential to change clinical practice for treating non-adherence. The provision of mHealth adherence interventions will have greater reach, especially to those at highest risk within pediatric epilepsy, reducing common barriers to behavioral health care. The study design will allow us to identify patients who are most likely to respond to interventions and step up care with more time- and resource-intensive interventions (i.e., therapist-guided telehealth sessions), when necessary. In the future, front-line health care providers, including nurses and social workers, could provide these therapist-assisted telehealth sessions. A tailored intervention that uses minimal resources will also maximize cost-savings. If efficacious, mHealth adherence interventions could be presented proactively to caregivers at diagnosis to promote high adherence behaviors initially, resulting in substantial cost-savings and prevention of poor health outcomes.

Our group conducted the first aims of this grant, in which we conducted focus groups and usability testing across the four sites to develop the Education microlearning sessions, Problem-solving module, and individualized adherence feedback reports with input from caregivers of young children with epilepsy. Their input provide significant feedback related to the design and infrastructure of the intervention, which directly informs this SMART trial.

4. STUDY DESIGN

We are conducting a sequential, multiple assignment, randomized clinical trial with caregivers of youth with epilepsy (n=600) in order to evaluate the efficacy and effectiveness of a mobile health adherence intervention to improve adherence to antiepileptic medications in children with newly diagnosed epilepsy. For the purposes of this protocol, CCHMC will serve as the Primary Site. The term “Collaborating Site” refers to external children’s hospital sites working in

collaboration with CCHMC on the study, including Medical University of South Carolina, Nationwide Children's Hospital, and Children's Hospital of Orange County.

5. DURATION

The anticipated duration of the study is approximately 5 years. The duration for participants is variable depending on their level of adherence during the baseline period and their enrollment date as the follow-up period was shortened twice to continue enrollment and allow participants to complete the study by the end of the grant period.

- For enrolled participants who achieve electronically monitored adherence >95% in the baseline period, their study participation will be approximately 2 months, with conclusion at the end of the baseline period.
- For participants with adherence < 95% in the baseline period, their participation will be:
 - 20 months (2 months baseline, 5 months of active intervention, and 13 months of follow-up) if they enrolled before 12/9/2022.
 - 14 Months (2 months baseline, 5 months of active intervention, and 7 months of follow-up) if they enrolled between 12/9/2022 and 3/8/2023.
 - 8 months (2 months baseline, 5 months of active intervention, and 1 month of follow-up) if they enroll after 3/8/2023.

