After completion of Stage 2, automated digital reminders will be turned off and adherence feedback reports will cease to be provided. Additional questionnaires will be completed via REDCap at Post-Treatment (1-Month Follow-Up in Month 8), Follow-Up 1 (6 months post-treatment in Month 14)*, and Follow-Up 2 (12 months post-treatment in Month 20)**.

Data collection procedures and measures: Participants will complete a demographic questionnaire that provides general information about the child's age, caregiver work history, family composition, socio-economic status, family history of seizures, history of seizures (e.g., type, who witness, when they occurred), and comorbid illnesses (e.g., learning disorders). In addition, caregivers will complete the questionnaires detailed in the table below.

Construct Measured	Respondent C=Caregiver; M=Medical Chart Review D=Doctor/Clinician	Stages and Time points			
		Baseline	Post (1 month post- treatment)	Follow-Up 1 (6 months post- treatment) *	Follow-Up 2 (12 months post- treatment) **
ORDER OF MEASURES (As applicable)					
Background Form (Demographic)	C	X			
Pediatric Epilepsy Medication Self-Management Questionnaire (PEMSQ) 
 PEMSQ: Self-reported Adherence 	C	X	X	X	X
Behavior Assessment System for Children-3 Parent-Rating Scales	C	X	X	X	X
Short Test of Functional Health Literacy in Adults	C	X	X	X	X
Pediatric Quality of Life in Epilepsy Module	C	X	X	X	X
Brief Symptom Inventory-18 (BSI-18)	C	X	X	X	X
Epilepsy Knowledge Questionnaire-Adapted (EKQ)	C	X	X	X	X

Social Problem-Solving Inventory-Revised Short (SPSI-Revised Short)	C	X	X	X	X
Pediatric Epilepsy Side Effects Questionnaire (PESQ)	C	X	X	X	X
Seizure Severity Scale Adapted for Children (SSSC)	C	X	X	X	X
Family Assessment Device (FAD)	C	X	X	X	X
Global Assessment of the Severity Scale of Epilepsy in Children (GASE)	D	X	X	X	X
Healthcare utilization	C	X	X	X	X
Medical Chart Review	M	X	X	X	X
Feasibility/Acceptability Questionnaire (FAQ)	C		X		
Impact of COVID-19 on Pediatric Epilepsy Management (ICPEM)	C	X	X	X	X

*Follow-Up 1 Questionnaires will only be completed by participants enrolled before 3/8/2023

**Follow-Up 2 Questionnaires will only be completed by participants enrolled before 12/9/2022

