8.1 Sample Size Considerations and Power Analysis: Power analysis was conducted based on SMART Stage 1, assuming ~180 participants randomized to treatment and ~90 to control group. Effect sizes for education-focused adherence interventions with reminders in other chronic conditions relative to controls (e.g., treatment as usual, pre-post) range from 0.08-0.20,^{72,170} while those with adherence feedback range from 0.78-1.03.^{80,171} Power for the primary analysis (Aim 1 below) will be 80% to detect a small-to-moderate standardized effect size (Cohen's $d=0.36$) and 97% to detect a moderate standardized effect size (Cohen's $d=0.50$). These detectable effect sizes reflect clinically meaningful changes in adherence. Power analyses require known and unknown assumptions, such as the anticipated response rate to Education + Automated Digital Reminders + Individualized Adherence Feedback at the end of Stage 1. Effect sizes for our face-to-face problem-solving adherence intervention, which incorporates IAF relative to treatment as usual, ranged from 0.95 (1st problem-solving session) to 1.59 (2nd problem-solving session).¹⁵ Assuming a 50% response rate to SMART Stage 1 treatment and a Bonferroni multiplicity adjustment, the proposed sample size provides 80% power with alpha at 0.05 to detect a standardized effect size of $d=0.69$ between any pair of embedded strategies (SMART Stage 2).

8.2. Data Analysis: All data analysis and management will also occur at North Carolina State University (NC State), which is the primary data analysis site. The Division of Behavioral Medicine and Clinical Psychology at CCHMC has developed a Divisional Data Core (DDC) in cooperation with the divisions of Biostatistics and Epidemiology and Bioinformatics to share the de-identified data with NC State. The CCHMC DDC will provide quality reports to audit the data routinely, provide data for safety monitoring committee reports for the biostatisticians at NC State, and cleaning of the data.

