**Epilepsy Adherence in Children and Technology (eACT): Fostering
Medication Adherence in Children With Epilepsy Using mHealth
Technology**

Clinicaltrials.gov NCT03817229

Unique Protocol ID: 2018-8411

Version 1.0-5/20/25

Power and Sample Size Estimation

Sample size estimation was informed by results of previous studies of adherence interventions. Effect sizes for education-focused adherence interventions with reminders in other chronic conditions relative to controls (e.g., treatment as usual, pre-post) range from 0.08-0.20 [42, 43], while those with adherence feedback range from 0.78-1.03 [44, 45]. Specifically, an HIV study found that individualized adherence feedback demonstrated a large, standardized effect size (Cohen's $d=0.78$) [44]. Similar and higher effect sizes have been found for mHealth interventions that include education, automated digital reminders, or individualized feedback in adult samples including asthma, diabetes, and heart disease (Cohen's $d=0.70-2.51$) [46-48].

Given the range of observed effect sizes and taking into account the size of clinically meaningful changes in adherence, sample size was determined to detect a small-to-moderate standardized effect size (Cohen's $d=0.36$) for the primary analysis of SMART Stage 1 comparing intervention to control with 80% power with significance level 0.05. Assuming 2:1 randomization to intervention vs control yields a conservative total sample size estimate of 270, with ~180 participants randomized to intervention and ~90 to control. This sample size leads to 97% power to detect a moderate standardized effect size (Cohen's $d=0.50$).

Power for the secondary analysis involving pairwise comparison of the intervention strategies embedded in the SMART is informed by effect sizes for our face-to-face problem-solving adherence intervention, which incorporates individualized adherence feedback relative to treatment as usual. These effect sizes ranged from from 0.95 (1st problem-solving session) to 1.59 (2nd problem-solving session). Power analyses for comparison of intervention strategies require additional unknown assumptions, such as the anticipated response rate to intervention at the end of Stage 1. Assuming a 50% response rate to SMART Stage 1 intervention and a Bonferroni multiplicity adjustment, the proposed sample size provides 80% power with significance level 0.05 to detect a standardized effect size of $d=0.69$ between any pair of the embedded intervention strategies #1 - #3.

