Secondary analyses will compare the mean outcomes associated with each of intervention strategies #1 - #3 embedded in the SMART on the basis of the outcomes adherence, seizure severity/frequency, HRQOL, and healthcare utilization at 1-, 6-, and 12-months post-intervention. Strategies #1 and #2 are non-adaptive intervention strategies in that intervention is not modified in accordance with Stage 1 adherence status (or any other participant characteristics), while #3 is an adaptive intervention strategy in that intervention is augmented by problem-solving in Stage 2 only under non-adherence in Stage 1. The pairwise comparison of the non-adaptive strategy #1 to the adaptive strategy #3 represents comparison of the least resource-intensive strategy (control) to the most resource-intensive strategy. Comparison of strategies #1, #2, and #3 will be carried out using specialized methods for SMART analysis based on inverse probability weighting for estimation of the mean outcome associated with a strategy that account for the fact that actual experiences of participants may be consistent with more than one strategy; for example, a participant who is randomized to intervention in Stage 1, is adherent in Stage 1 (i.e., is a responder to intervention), and continues to receive intervention in Stage 2 is consistent with having followed either embedded strategy #2 or #3. In this case, a participant's data contributes to assessment of improvement in outcome for both strategies. For each strategy, the inverse probability weighting is by the reciprocal of the estimated probability that a participant's experience is consistent with the strategy. We will conduct pairwise comparisons of the three embedded strategies using these methods based on adherence, seizure severity/frequency, HRQOL, and healthcare utilization at 1, 6-, and 12-months post-intervention. We will also conduct a global test of the null hypothesis that the mean outcomes associated with the three strategies are the same versus the alternative that at least one mean differs from the others.

Exploratory Analysis Plan:

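### The single Aim 2 power figure (80% at d=0.69, based on 180/90) cannot be carried over to the 6- and 12-month comparisons, because follow-up was cut by enrolment date and the figure was not revised

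*Protocol*

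**What the plan says.** **Follow-up.** Protocol section 5 states that "the follow-up period was shortened twice to continue enrollment and allow participants to complete the study by the end of the grant period". Randomized families have 13 months of follow-up if enrolled before 12/9/2022, 7 months if enrolled between that date and 3/8/2023, and 1 month if enrolled later. The footnotes to the measures table in section 8 agree: "Follow-Up 2 Questionnaires will only be completed by participants enrolled before 12/9/2022", with the matching restriction to before 3/8/2023 for the 6-month visit. Because section 5 shortens participation itself, monitored adherence is affected as well as the questionnaires.

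**Analysis.** Protocol section 8.2 (Aim 2) and the SAP's Secondary Analysis Plan compare the three embedded strategies on adherence, seizure outcomes, quality of life and "healthcare utilization at 1-, 6-, and 12-months post-intervention". The SAP estimates each strategy mean by inverse probability weighting.

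**Power.** The SAP supposes that half of the Stage 1 intervention group responds, corrects for multiplicity by Bonferroni, and on that footing claims that "the proposed sample size provides 80% power with significance level 0.05 to detect a standardized effect size of $d=0.69$ between any pair". The claim covers strategies #1 to #3. The sample is the primary-analysis one, "with ~180 participants randomized to intervention and ~90 to control". Protocol section 8.1 makes the same claim and labels it SMART Stage 2. Neither sentence names a follow-up month. The only loss allowed for after randomization is 10% during Stage 1.

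**Revision.** The SAP reports that planned enrolment fell from 600 to 450 after the COVID-19 suspension, keeping 180/90. Its power, analysis and missing-data sections do not mention the shortened follow-up.

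**The concern.** The power figure uses all 180/90 families, but the plan itself schedules fewer of them for the 6-month visit and fewer still for the 12-month visit. Since the strategy comparisons are listed at 1, 6 and 12 months and only one figure is given, a reader will naturally apply 80% to each.

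Two readings of the results are at stake. A null finding at 6 or 12 months would be weighed against a power that was never worked out for the families who had that visit. And because the three time points rest on nested, shrinking cohorts, a smaller contrast at 12 months than at 1 month could reflect fading of the effect, a change in who is measured, or both.

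**Working it through.** **Inputs from the documents.** 180/90; 50% response to the Stage 1 intervention; Bonferroni adjustment of 0.05; d=0.69; 80% power.

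**Assumptions.** The second randomization is 1:1 (ratio not stated). Bonferroni is over three pairwise comparisons (divisor not stated), so alpha = 0.05/3 = 0.0167. Tests are two-sided (stated for the primary analysis only). Outcome variance is common, and loss is equal across arms. The share f of families enrolled early enough for a visit is not in the documents, so it is varied.

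**1. Reproducing the stated figure.** Non-responders: 180 × 0.50 = 90, split into 45 v 45. A two-sample t-test at 0.0167 with d=0.69 has 79.5% power (81.0% by the normal approximation), and the d detectable with 80% power is 0.69. Without Bonferroni the power would be 90%; with a divisor of 2, about 84%. The stated figure therefore matches a 45 v 45 comparison of re-randomized non-responders with a divisor of 3.

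**2. The same set-up with 45 × f per group (t-test).**

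| f | n per group | power at d=0.69 | d at 80% power |
|---|---|---|---|
| 1.00 | 45 | 79.5% | 0.69 |
| 0.97 | 43.7 | 78% | 0.70 |
| 0.90 | 40.5 | 74% | 0.73 |
| 0.70 | 31.5 | 61% | 0.84 |
| 0.50 | 22.5 | 44% | 1.00 |

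There is no slack: any loss takes power below the stated value.

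**3. The planned weighted strategy means.** For #2 or #3, 90 responders carry weight 1 and 45 non-responders carry weight 2. The weights sum to 90 + 90 = 180 and their squares to 90 + 180 = 270, so the variance of the mean is 270/180² = 1/120 in units of the outcome variance. For #1 it is 1/90. For #1 v #3:

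SE = sqrt((1/90 + 1/120)/f) = 0.1394/sqrt(f)

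Power = Φ(0.69/SE − 2.394)

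| f | power at d=0.69 | d at 80% power |
|---|---|---|
| 1.00 | 99.5% | 0.45 |
| 0.70 | 96% | 0.54 |
| 0.50 | 87% | 0.64 |
| 0.40 | 77% | 0.71 |

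Power reaches 80% at f = ((2.394 + 0.842) × 0.1394/0.69)² = 0.43. With a t reference distribution on effective sizes 90 and 120 it is 0.44. So 80% is kept until roughly 56% to 57% of families lack the visit.

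**4. What does not depend on the basis.** The standard error scales with 1/sqrt(f), so the detectable difference grows by about that factor: 1.05 at f=0.90, 1.20 at 0.70 and 1.41 at 0.50.

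**The case against.** A reader might infer that 80% power is impossible at 6 and 12 months, or that the sponsor's arithmetic is wrong. The documents support neither. The figure reproduces. No counts by enrolment date are given, so the loss may be small or large. The power sentence names no month, and the protocol ties it to Stage 2, so nowhere is 80% explicitly claimed at 12 months. And on the weighted strategy means that the SAP will actually use, #1 v #3 tolerates the loss of more than half the families at d=0.69. All of that stands, and it rules out quoting the 45 v 45 percentages alone as the size of the problem.

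The SAP's missing-data section also has a route for more than 10% missingness: weighting by the probability that the outcome is observed, given baseline and earlier variables. This partly covers unscheduled visits. It restores no power, however, and it does not distinguish a visit that was never scheduled from a family that dropped out.

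A reader might also infer that the later contrasts are biased or that early and late enrollees differ. The cut-offs follow calendar date, not arm, so each contrast at a given time point remains randomized. Nothing in the documents shows that the cohorts differ, and no test of fading over time is planned. What remains is a caution about comparing time points.

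The objection does not remove the gap. The SAP introduces the figure as power for the secondary pairwise comparisons, and it places those comparisons at 1, 6 and 12 months. It postdates both cuts and restates the full-sample figure without qualification.

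**Conclusion.** The point holds as a limit on what the stated figure covers. The 80% at d=0.69 describes a full 180/90 sample and should not be read as applying to the 6- or 12-month comparisons, for which the documents give neither an expected number nor a detectable difference.

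The size depends on an unknown share. On the basis that reproduces the figure, power falls to 74%, 61% and 44% at 90%, 70% and 50% eligible. On the planned weighted analysis, #1 v #3 stays at or above 80% until roughly 56% of families lack the visit. On either basis precision is lost in proportion to 1/sqrt(share eligible). These results rest on the assumptions listed with the calculation; attrition after Stage 1 would lower power further. The primary analysis, at the end of Stage 1, is not affected.

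**What to change.** - **SAP Power and Sample Size Estimation, and protocol 8.1:** limit the d=0.69 sentence to the full-sample (1-month) comparison. For 6 and 12 months, state the number randomized by arm who enrolled before each cut-off, and the difference detectable with that number under the planned weighted analysis.
- **SAP Handling of Missing Data:** treat visits not scheduled because of enrolment date separately from dropout, and say how each enters the weighting. Settle which group a family enrolled on 3/8/2023 itself belongs to, since sections 5 and 8 of the protocol word that boundary differently.
- **Reporting:** beside the 6- and 12-month results, show the 1-month contrast in the same early-enrolled families, so that persistence is read within one cohort.

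The cost is SAP and protocol wording and one extra table from data already held. The stated power or detectable difference becomes less favourable at 6 and 12 months. No new participants are needed.
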